6. Plan for reporting UPIRSOs (including Adverse Events) to the IRB

The principal investigator will report the following types of events to the IRB:

Any incident, experience or outcome that meets ALL 3 of the following criteria:

1. Is unexpected (in terms of nature, specificity, severity, or frequency) given (a) the research procedures described in the protocol-related documents, such as the IRB-approved protocol and informed consent document and (b) the characteristics of the subject population being studied; AND
2. Is related or possibly related to participation in the research (*possibly related* means there is a reasonable possibility that the incident, experience, or outcome may have been caused by the procedures involved in the research); AND
3. Suggests that the research places subjects or others at greater risk of harm (including physical, psychological, economic, legal, or social harm) than was previously known or recognized.

Unanticipated Problems Involving Risks to Subjects or Others (UPIRSOs) may be medical or non-medical in nature, and include – but are not limited to – *serious, unexpected, and related adverse events* and *unanticipated adverse device effects*. **Please note** that adverse events are reportable to the IRB as UPIRSOs **only** if they meet all 3 criteria listed above.

These UPIRSOs/SAEs will be reported to the IRB in accordance with IRB Policy 710, using the appropriate forms found on the website. All related events involving risk but not meeting the *prompt* reporting requirements described in IRB Policy 710 should be reported to the IRB in summary form at the time of continuing review. If appropriate, such summary may be a simple brief statement that events have occurred at the expected frequency and level of severity as previously documented. In lieu of a summary of external events, a current DSMB report can be submitted for research studies that are subject to oversight by a DSMB (or other monitoring entity that is monitoring the study on behalf of an industry sponsor).

13. Statistical Considerations: Describe the statistical analyses that support the study design.

Data analysis will be conducted in collaboration with [name] at the Yale Center for Analytic Sciences. For Aim 1, we will require 25 T1DM aware and 25 healthy controls to provide 80% power to detect differences of 0.013 between them and the T1DM-Unaware subjects at the Bonferroni corrected 0.017 significance level. This sample size will also provide 80% power at the 0.01 level of significance to detect a difference of 0.22 for average brain glucose for Aim 2. We will enroll 27 aware and 27 healthy controls to accommodate a potential

5% inadequate scan rate. The T1DM Unaware group sample size (n=40) was first determined to provide sufficient power for Aim 3. T1DM Aware and healthy control sample sizes were then estimated based on power for aims 1 and 2. Our preliminary data shows differences in the co-primary outcome of average brain glucose between those with a low glucose variability index and those with a high glucose variability index of 0.455 (SD=0.26). We've also observed a difference of 0.013 (SD=0.016) in our other co-primary outcome change in brain activity from hypoglycemia to euglycemia in the striatum between T1DM Aware and Unaware. Thus, for Aim 3 a sample size of 20 T1DM Unaware subjects per arm will provide 80% power to detect a difference of 0.22 in brain glucose and 0.013 in change in brain activity. We will enroll 65 Unaware for Aim 3 in order to accommodate a potential 10% dropout rate.

Aim 1 Analysis: Comparison of brain activity between groups will be performed using a repeated measures mixed model. The outcome will be brain activity in our primary region of interest, the caudate region of the striatum. Fixed factors for group (unaware, aware, HC), glucose category (eugly, mild hypo, moderate hypo) and their interaction will be included. Linear contrasts comparing changes in brain activation from euglycemia to moderate hypo between groups will be estimated and evaluated at the 0.017 Bonferroni corrected significance level. Secondary analyses will examine other promising ROIs (hypothalamus and prefrontal cortex). Similar analyses will be done to assess group differences in resting state connectivity and hormones.

Aim 2 Analysis: Comparisons of glucose levels in specific brain regions will be made using a repeated measures mixed model. Fixed factors include group and glycemic state (e.g. acute hyperglycemia) and their interaction. A random effect for subject will be used to accommodate correlation between repeated assessments. Linear contrasts comparing differences in average brain glucose between groups will be estimated. A significance level of 0.01 will be used to accommodate multiple pairwise comparisons of groups. Similar secondary analyses will be conducted to assess differences in V_{TCA} between groups and fructose production during hyperglycemia. For the rodent studies our preliminary data showed a 1.5 standardized difference in fructose and glutathione concentrations between groups, so a sample size of 14-15 rats per group will provide 80% power to detect a large standardized difference in study outcomes at the two-sided 0.05 significance level. Between-group comparisons, ANOVA and t-tests will be used for continuous variables, where applicable.

Plan for Missing Data: Prevention is the obvious way to control for bias and loss of power from missing data (71). We will follow the intent to treat principle, requiring follow-up of all subjects regardless of treatment³⁴. Postcard and telephone visit reminders will be sent and alternative contacts identified to minimize loss to follow-up. Timely data entry and weekly missing data reports will trigger protocols for obtaining missing data items. Despite these efforts it is reasonable to assume missing data will occur most likely at random³⁵. We will evaluate the plausibility of this assumption using logistic regression to identify factors linked to dropout.

SECTION II: RESEARCH INVOLVING DRUGS, BIOLOGICS, RADIOTRACERS, PLACEBOS AND DEVICES

If this section (or one of its parts, A or B) is not applicable, check off N/A and delete the rest of the section.

A. RADIOTRACERS N/A

B. DRUGS/BIOLOGICS N/A

1. Use of Placebo: Not applicable to this research project

2. Continuation of Drug Therapy After Study Closure Not applicable to this project

B. DEVICES N/A

1. Are there any investigational devices used or investigational procedures performed at Yale-New Haven Hospital (YNHH) (e.g., in the YNHH Operating Room or YNHH Heart and Vascular Center)? Yes No

If Yes, please be aware of the following requirements:

A YNHH New Product/Trial Request Form must be completed via EPIC: Pull down the Tools tab in the EPIC Banner, Click on Lawson, Click on “Add new” under the New Technology Request Summary and fill out the forms requested including the “Initial Request Form,” “Clinical Evidence Summary”, and attach any other pertinent documents. Then select “save and submit” to submit your request; AND

Your request must be reviewed and approved **in writing** by the appropriate YNHH committee before patients/subjects may be scheduled to receive the investigational device or investigational procedure.

2. **Background Information:** Provide a description of previous human use, known risks, and any other factors that might influence risks. If this is the first time this device is being used in humans, include relevant data on animal models.

The FreeStyle Libre Glucose Monitoring System is a continuous glucose monitoring (CGM) device indicated for the management of diabetes in persons age 18 and older. It is designed to replace blood glucose testing for diabetes treatment decisions. The System detects trends and tracks patterns aiding in the detection of episodes of hyperglycemia and hypoglycemia, facilitating both acute and long-term therapy adjustments. Interpretation of the System readings should be based on the glucose trends and several sequential readings over time. The System is intended for single patient use and requires a prescription.

The CGM poses no major risks to the subjects. Participants may feel a mild discomfort (pin prick sensation) during the sensor insertion. Some individuals may experience black and blueness of the skin at the insertion site of the CGM sensor, which resolves by itself in a few days. Redness and discomfort (inflammation) can occur at the sensor insertion site. Rarely sensors may fracture and a small piece may remain under the skin which will need to be removed by a study clinician. This may cause mild discomfort, bruising, or temporary bleeding.

3. **Source:**

- a) Identify the source of the device to be used. Abbott
- b) Is the device provided free of charge to subjects? Yes No

4. **Investigational device accountability:** State how the PI, or named designee, ensures that an investigational device is used only in accordance with the research protocol approved by the HIC, and maintains control of the investigational device as follows:

- a) Maintains appropriate records, including receipt of shipment, inventory at the site, dispensation or use by each participant, and final disposition and/or the return of the investigational device (or other disposal if applicable): Electronic records (shipment receipts, inventory, participant use, return of device) will be stored in the study folder on the secured server on a password protected computer or laptop, which is kept in the PI's locked office. Any paper records will be scanned and stored in the file as well.
- b) Documents pertinent information assigned to the investigational device (e.g., date, quantity, batch or serial number, expiration date if applicable, and unique code number): Pertinent information assigned to the investigational device will be stored in an electronic file in the study folder on the secured server on a password protected computer or laptop, which is kept in the PI's locked office.

- c) Stores the investigational device according to the manufacturer's recommendations with respect to temperature, humidity, lighting, and other environmental considerations: Per the manufacturer's recommendations, the sensor kit will be stored in a location between 39-77 degrees Fahrenheit and between 10-90% non-condensing humidity. There are no other environmental considerations.
- d) Ensures that the device is stored in a secure area with limited access in accordance with applicable regulatory requirements: The sensor kit will be stored in the PI's locked office in a locked cabinet.
- e) Distributes the investigational device to subjects enrolled in the IRB-approved protocol: The device will be provided to subjects enrolled in this IRB-approved protocol after consent has been obtained and a study clinician has explained how to use the device and has determined that the subject understands how to use the device. Sufficient time will be provided in order for the subject to ask any questions they may have about the device and feel confident in using the device. The participants will be given one of the study physician or nurse practitioner's cell phone number to contact for any questions, concerns or problems.

SECTION III: RECRUITMENT/CONSENT AND ASSENT PROCEDURES

1. Targeted Enrollment: Give the number of subjects:

- a. Targeted for enrollment at Yale for this protocol: 150
- b. If this is a multi-site study, give the total number of subjects targeted across all sites: N/A

2. Indicate recruitment methods below. Attach copies of any recruitment materials that will be used.

 Flyers	 Internet/web postings	 Radio
 Posters	 Mass email solicitation	 Telephone
 Letter	 Departmental/Center website	 Television
 Medical record review*	 Departmental/Center research boards	 Newspaper
 Departmental/Center newsletters	 Web-based clinical trial registries	 Clinicaltrials.gov
 YCCI Recruitment database	 Social Media (Twitter/Facebook):	
 Other:		

* Requests for medical records should be made through JDAT as described at <http://medicine.yale.edu/ycci/oncore/availableservices/datarequests/datarequests.aspx>

3. Recruitment Procedures:

- a. Describe how potential subjects will be identified.

Potential subjects will be identified as indicated below using the methods identified in #2 above:

- Self-Identify
- Provider Referrals
- Study Team Members
- Existing registries, studies, and websites where participants have previously provided informed consent or a request to be contacted for research utilizing their preferred method of contact when known.
- Joint Data Analytics Team (JDAT)

How these options will be utilized is further described in section "b" below.

- b. Describe how potential subjects are contacted.

- Self-Identify and Provider Referrals: Participants will self-identify using IRB approved recruitment materials that will be posted locally. Recruitment materials will display the contact information of the study team in addition to a description of the study. Potential participants may also be approached by their medical

provider. Additionally, participants may be approached by study personnel at community events, or at various locations where potentially eligible patients are seen when facilitated through the participant's treatment team, including at Yale SOM, YNHH, YMG, and VA Connecticut Healthcare System. These sites include the Adult Endocrine Clinic/Yale Diabetes Center (YDC), community clinics and Yale University Health.

- Recruitment through Existing Registries and Studies: In addition, the YDC diabetes registry will be used to identify eligible patients and contact them with IRB approved materials by phone, email or traditional mail (letter), since this category of patients has already given their consent to be contacted for potential trials. Furthermore, participants will be recruited through the YCCI website/registry/Help Us Discover and ClinicalTrials.gov website. Participants may also be identified through their previous participation in HIC #0108012609, 2000021046, 2000020059, 2000020041 and 1408014461.

Study personnel will use MyChart, traditional mail, telephone or email of patients recruited through this method. If the EPIC registration module provides a preferred method of contact, that method will be utilized. If the participant is not registered in EPIC but has expressed interest in a research study by calling, emailing, filling out an online questionnaire, or speaking with study personnel face-to-face, the patient will be contacted by their means of preference, if stated.

- Recruitment through JDAT: The Joint Data Analytics Team (JDAT) will also be used to query eligible patients in EPIC based on the eligibility criteria outlined above (#8). JDAT will also be used to identify potential subjects with the various permutations of diagnosis codes related to type 1 diabetes. JDAT will identify and send a study communication to potential participants based on these criterion that fall within the following time period: the last 2 years. Potential participants who do not use MyChart will receive a paper mailing including information about the study.

JDAT will not identify the potential participants to the researchers, and therefore the researchers will receive no identifiable information from JDAT.

- Messaging to Study Participants:

The following wording will be used in the letter or MyChart message patients receive via JDAT describing the study and inviting them to participate:

- "You are receiving this notification because you may qualify and be interested in a study looking at mechanisms for restoration of hypoglycemia awareness. The Yale New Haven Health electronic health record system has searched medical conditions to find people who may be good matches for research studies. No one has looked at your record and no information has been shared with any research doctor or research team member. Just because you received this message does not mean that you are in a research study or that you have to decide to be in this or any study. You may be interested and eligible to participate in a research study conducted by Yale University investigators to better understand diabetes.

To opt-out of research, including opting out of receiving future messages about research studies, please email [contact] or call [name] and select option #3.

Title of study: Mechanisms for restoration of hypoglycemia awareness

Principal Investigator: [name], MD

Study Coordinator: [name]

[contact]

The message/mailing to potential study participants will also include the following information, regardless of who sends it:

- "You are receiving this notification because you may qualify and be interested in a study looking at mechanisms for restoration of hypoglycemia awareness. Approximately 65 subjects will be enrolled in this study.

Description of Study:

Aim 1: Determine the impact of frequent hypoglycemia and hypoglycemia unawareness on brain responses to visual food cues as well as brain functional connectivity in T1DM patients.

Aim 2: Assess the Impact of antecedent bouts of hypoglycemia on brain glucose transport/metabolism during hyperglycemia in T1DM Unaware, T1DM Aware as well as healthy controls using 1H, 13C magnetic resonance spectroscopy (MRS).

Aim 3: Determine if reducing hypoglycemia and glycemic variability using CGM reverses altered brain glucose transport/metabolism and functional connectivity in hypoglycemia unaware T1DM patients.

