endogenous insulin secretion; 2) secretion of counterregulatory hormones and 3) subjective awareness of hypoglycemia provoking carbohydrate ingestion. A small decline in glucose (low 70 mg/dl range) initially acts to suppress insulin secretion, which is followed by glucagon and catecholamine release (at 65-69mg/dl) that act in concert to restore euglycemia by stimulating hepatic glucose production and diminishing glucose uptake. Other anti-insulin hormones (e.g. GH and cortisol) come into play somewhat later to enhance and help sustain counter regulation. If glucose falls further (<60-64mg/dl) autonomic and neuroglycopenic symptoms appear, triggering food ingestion. Thus, severe hypoglycemia is rare clinically in the absence of diabetes. In T1DM, this defense system is interrupted at every level. The loss of endogenous insulin and reliance on exogenous insulin make suppression of plasma insulin impossible. Beta cell loss is also closely linked to loss of glucagon responses to hypoglycemia as well, a stimulus specific defect that rapidly appears in nearly all T1DM patients ⁷⁻⁹. Thus, T1DM patients are very vulnerable to reduced catecholamine release; a scenario associated with intensive insulin therapy, long disease duration, and in particular antecedent hypoglycemia events ¹⁰⁻¹⁶. Loss of adrenomedullary responses appears to be in large part a functional disorder linked to iatrogenic hypoglycemia, since hypoglycemia avoidance commonly reverses the defect ^{17,18}.

The effects of recurrent hypoglycemia, intensive insulin therapy and hypoglycemia unawareness on cognitive function in T1DM patients during hypoglycemia are somewhat controversial with studies reporting differing results. Specifically, it remains uncertain whether the effect of intensive insulin therapy to lower the glucose level needed to activate adrenomedullary responses is mirrored identically by changes in the threshold needed to impair cognitive function, many support this view ¹⁹⁻²², but not all studies ^{23,24}. Thus, while T1DM patients with a history of frequent hypoglycemia often require a greater glucose fall before cognitive impairment develops, there is some response variability. On the other hand, patients with hypoglycemia unawareness appear to show a more profound disturbance in higher cognitive function than T1DM controls who maintain awareness during acute hypoglycemia ²⁵.

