2. Continuous glucose monitoring (CGM) placement: For up to 14 days, all eligible subjects will be asked to wear a blinded continuous glucose monitor (FreeStyle Libre Pro). Given that this data is blinded, patients will be informed that it is not a replacement for self-monitoring of blood glucose. Subjects should continue their normal testing routine while wearing the sensor. CGM placement will take place at the HRU or CSRU. Those not already using CGM in their usual care will be trained in its proper use by experienced study staff. Patients already using CGM will be allowed to use their usual CGM, however, they will also be asked to wear a second blinded study sensor. Subjects will be provided with our contact information in the event that they have any questions, concerns or issues related to the CGM. Intense exercise may cause the sensor to loosen due to sweat or movement of the sensor. If the CGM sensor falls off while the subject is wearing it, we will ask them to return to the HRU or CSRU so that a new sensor can be re-inserted.

The CGM consists of a sensor that measures glucose levels from the interstitial tissue. The sensor is sterile and comes in an unopened package. It has a plastic wire-like tip that is placed under the skin and continuously measures the glucose levels. A trained study staff member will insert the CGM wire-like tip under the volunteer's skin with the use of the CGM sensor insertion kit. Each sensor is single use only and disposable. The FreeStyle Libre Pro does not require any calibration, as is the case with other CGM devices. This means that no finger sticks are required for its use.

- a. Hypoglycemia questionnaires: All T1DM participants will be asked to complete questionnaires assessing hypoglycemia at the time of the CGM placement. The responses to these questionnaires and the questionnaires during the fMRI scan described below, in addition to analysis of the counterregulatory hormones obtained during the fMRI scan, will be used to categorize T1DM participants as either aware (T1DM-A) or unaware (T1DM-UA).
- b. Neurocognitive questionnaires: We will collect metrics of education level and neurocognitive function amongst all participants at the time of the CGM placement to assess executive function, episodic memory language, processing speed, working memory and attention.

3. CGM removal:

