After 14 days of wearing the CGM, it will be removed by a trained study staff member. To remove the sensor, the adhesive patch will be gently peeled off from the skin, together with the sensor. Removal of the sensor is a painless procedure. The sensor will be discarded after use.

Note regarding order of visits: CGM placement will occur up to 14 days prior to the subject's first scan (fMRI or MRS). CGM removal will occur on the same day as the subject's first scan (fMRI or MRS). Due to the many complexities of scheduling, although the fMRI is part of Aim 1, the subject may have the MRS scan done first, which is part of Aim 2. The order of scans in no way effects subject safety or research integrity. T1DM subjects will have a second CGM placed after the first scan and will wear this CGM until the second scan, where it will be removed. Therefore, T1DM subjects will wear the CGM two times, once before each scan for up to 14 days prior.

4. fMRI Scan with hyperinsulinemic euglycemia-mild hypoglycemia clamp: All subjects will arrive on the morning of the scan at 7AM following an 8-hr fast. T1DM subjects will be instructed to continue their home insulin regimen until they arrive at the Yale Magnetic Resonance Research Center (MRRC) that is equipped with infusion rooms for IV and line placements. A urine pregnancy test will be performed on all women of childbearing potential, and women who are pregnant will be excluded. Following IV placements and baseline blood collections at ~8 AM subjects will receive an insulin infusion (2 mU/kg/min) together with a variable glucose infusion to keep glucose levels at ~100-110 mg/dl. Once glucose levels are stabilized outside the magnet (~45 min), they will be transferred into the MRI for a 2-step hyperinsulinemic euglycemic (90-100 mg/dl)-mild hypoglycemic (55-60 mg/dl) clamp. Initially, baseline structural scans will be obtained, followed by blood oxygen level dependent (BOLD) contrast acquisitions during visual cues and cognitive tasks. At each clamp step, participants will also be asked to complete questionnaires assessing hypoglycemia. Plasma glucose will be measured every 5-10 min. Throughout, blood will be obtained for insulin, glucagon, cortisol, catecholamines and other hormonal and metabolic blood tests. A1c will also be measured at this visit.

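### Clamp hormones help assign the Aware/Unaware label and are then tested between the groups so labelled, so the Aim 1 hormone p-values do not hold their nominal level

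*Combined protocol and SAP*

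**What the plan says.** Research Plan, Aim 1, item 2a builds the label from three sources: questionnaires at CGM placement, questionnaires during the fMRI clamp, and hormones from that same clamp. The last two, "in addition to analysis of the counterregulatory hormones obtained during the fMRI scan, will be used to categorize T1DM participants as either aware" or unaware. No weights, cut-offs or combining rule are given.

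Item 4 lists what is drawn at the clamp: "Throughout, blood will be obtained for insulin, glucagon, cortisol, catecholamines and other hormonal and metabolic blood tests". Insulin is infused. The others named are those that the Background describes as the counterregulatory response: "followed by glucagon and catecholamine release (at 65-69mg/dl) that act in concert to restore euglycemia", and "Other anti-insulin hormones (e.g. GH and cortisol) come into play somewhat later to enhance and help sustain counter regulation".

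Statistical Considerations, Aim 1 Analysis, makes caudate activity the outcome of a mixed model with group at three levels (unaware, aware, healthy control). It then adds: "Similar analyses will be done to assess group differences in resting state connectivity and hormones". It does not exclude the hormones that classified the subjects, and it does not call the comparison descriptive.

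A label free of hormones is available. Item 2a states: "All T1DM participants will be asked to complete questionnaires assessing hypoglycemia at the time of the CGM placement". The note on visit order adds that "CGM placement will occur up to 14 days prior to the" subject's first scan.

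**The concern.** If a hormone value helps decide which group a subject joins, testing that value between the groups partly tests the sorting rule. The usual null distribution no longer applies, because the groups were formed by looking at the outcome.

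The problem reaches further than Aware vs Unaware. Controls are not sorted on hormones, but the two T1DM groups are. Sorting pushes the Unaware mean down and the Aware mean up, so each contrast with controls moves as well.

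A reported hormone gap would naturally be read as the loss of counterregulation that accompanies unawareness. Part of it would come from the grouping rule, and the p-value attached to it could not be interpreted.

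**Working it through.** **The plan's own figures.** It gives none for hormones. Its Aim 1 power is for caudate activity: 0.013 / (0.016 × √(1/25 + 1/40)) = 3.19; minus 2.39 (two-sided 0.017, sidedness assumed) this is 0.80, so power is 78.8% against the stated 80%. That reproduces, but has no bearing on this point.

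**Inputs from the protocol.** 25 Aware and 40 Unaware; 0.017, which is set for the caudate contrasts only, so 0.05 is also shown.

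**Assumptions, not in the documents.** Q (placement questionnaire), S (in-scan questionnaire) and H (hormone change from euglycemia to hypoglycemia) are standard normal with common correlation r. The score is (1−2w)Q + wS + wH, with w = 0.1, 0.2 or 1/3. The lowest 40 of 65 are Unaware.

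**Formula.** Sorting 65 subjects on H alone and splitting 40/25 gives a mean gap in H of 1.596 SD. Sorting on any other normal score gives 1.596 × corr(H, score). Here

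corr = [r(1−w) + w] / √[(1−2w)² + 2w² + 2r(2w(1−2w) + w²)].

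Example, r = 0.5, w = 0.1: 0.55 / √0.83 = 0.604, and 1.596 × 0.604 = 0.96 SD. Simulation with 20,000 replicates agrees throughout.

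**Step 1: the test level (r = 0).** The hormone is unrelated to the other items, so every rejection is produced by the label.

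| w | Gap, SD | Rejects at 0.05 | Rejects at 0.017 |
|---|---|---|---|
| 0.1 | 0.20 | 12% | 5% |
| 0.2 | 0.48 | 48% | 31% |
| 1/3 | 0.92 | 98% | 95% |

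If three hormones share the weight w equally, the part due to one hormone's own contribution is 0.07 to 0.35 SD, with rejection of 6% to 28% at 0.05.

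**Step 2: contrasts with controls (r = 0, w = 1/3).** The 0.92 SD gap splits around the overall mean: Unaware −0.92 × 25/65 = −0.35 SD, Aware +0.92 × 40/65 = +0.57 SD. With 25 controls whose mean equals that of T1DM overall, tests at 0.05 reject about 32% (Unaware) and 55% (Aware) of the time. At w = 0.1 the rates are only 6–7%.

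**Step 3: size against the true gap.** Suppose that the common correlation arises from one trait, awareness, on which each item loads √r. A perfect label on that trait gives a gap of 1.596√r. The placement questionnaire alone gives 1.596r.

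| r | Perfect label | Composite, w = 0.1 / 0.2 / 1/3 | Placement questionnaire only |
|---|---|---|---|
| 0.3 | 0.87 | 0.68 / 0.90 / 1.17 | 0.48 |
| 0.5 | 1.13 | 0.96 / 1.13 / 1.30 | 0.80 |
| 0.7 | 1.33 | 1.23 / 1.33 / 1.43 | 1.12 |

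The composite gap is too small at w = 0.1, about right at w = 0.2 and too large at w = 1/3. Two errors oppose each other: misclassification shrinks the gap, and selection on the hormone widens it.

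**The case against.** The strongest reply is that hormones are a legitimate part of defining unawareness and that a real gap is likely. The Background describes reduced catecholamine release as "a scenario associated with intensive insulin therapy, long disease duration, and in particular antecedent hypoglycemia events". Both points stand. They are reasons to keep the composite label, but they do not make a test of a defining variable valid.

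A second reply is that the matter is minor. Hormones appear in no stated Aim, are not co-primary, and carry no sample size. The 98% figure belongs to an extreme case with uncorrelated components. If three hormones share the weight, each one's own part is only 0.04–0.13 SD at r = 0.5 and 0.02–0.07 SD at r = 0.7. That limits the weight of the point, but the protocol does not say which case applies.

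A reader might infer that the hormone gap must be exaggerated. The documents do not support this. The composite does exceed the placement-questionnaire gap, by 0.96 − 0.80 = 0.16 to 1.30 − 0.80 = 0.50 SD at r = 0.5. But that comparator is itself attenuated by misclassification, and against a perfect label the sign of the error depends on a weight that is not given.

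A reader might also infer that the primary Aim 1 result is circular. It is not in this sense: neither caudate activity nor brain glucose enters the label.

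**Conclusion.** The point holds for the hormone contrasts. The circularity follows from the text: clamp hormones define the groups, and hormones are then tested between them. For every hormone that contributes to the label, the Aware-vs-Unaware p-value does not hold its level, and both contrasts with healthy controls are shifted.

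The size is not determined by the documents. The rejection rates rest on an assumed linear score, forced group sizes and zero correlation. The comparison with the true gap rests on an assumed single shared trait. Neither the magnitude nor the net direction of the bias can be stated without the classification rule. A hormone that plays no part in the label, and is unrelated to those that do, would escape, but the protocol does not identify any.

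This is a defect in a secondary analysis that should be corrected. It does not threaten the co-primary analyses.

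**What to change.** In Research Plan, Aim 1, item 2a, name the hormones that classify. In Statistical Considerations, Aim 1 Analysis, add:

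> For hormones used to assign Aware/Unaware status, all group contrasts that use the composite label (Aware vs Unaware, and each against healthy controls) will be reported descriptively, without significance tests. Any inferential hormone comparison involving the Aware or Unaware groups will use status taken only from the CGM-placement questionnaires, by a scoring rule fixed before any scan.

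The composite label and the co-primary analyses stay as they are. No new data are needed.

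Costs:
- The hormone contrasts lose their p-values under the composite label.
- A scoring rule for the placement questionnaires must be written, since the protocol gives none. The sub-study text refers to subjects already enrolled; if scans have taken place, the rule should at least be fixed without sight of hormone results.
- The study will carry two Aware/Unaware groupings. About 3 to 12 of 65 subjects change group at an assumed correlation of 0.5.
- The questionnaire-only gap is conservative. Under the shared-trait assumption it understates the awareness gap by 0.87 − 0.48 = 0.39 SD at r = 0.3, 1.13 − 0.80 = 0.33 at 0.5 and 1.33 − 1.12 = 0.21 at 0.7. The report should say so.
- Power is lower. With 25 vs 40, 80% power needs a gap of 0.73 SD at 0.05 or 0.84 SD at 0.017. Power at 0.05 is about 48% at r = 0.3, 92% at 0.5 and above 99% at 0.7.
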